#### 5.4.1.2 Main analytical approach

The time from the first dose of TM BUP to treatment discontinuation will be presented by induction arm using Kaplan-Meier (KM) curves within the randomisation strata (UDS fentanyl negative vs. positive at the day of first dose of TM BUP) and for overall. Retention rate (with 95% confidence interval [CI]) at 5 weeks (35 days) will be estimated using KM product limit method for each induction arm within the randomisation strata and for overall. Hazard ratio (with 95% CI) of RBP-6000 RI to SoC induction will be estimated using a Cox proportional hazard model, with treatment arm as a single covariate, stratified by the randomisation strata. KM plots by treatment arm and by treatment arm and fentanyl UDS subpopulation will be produced.

#### 5.4.1.3 Exploratory analysis approach

The completion rate for the OLIS (ie, receiving double-blind RBP-6000 Injection 3) will be estimated by Bayesian beta-binomial model using non-informative uniform prior, ie, Beta (1,1), within individual induction arms. The posterior distribution of completion rate difference between the 2 arms will be obtained and presented in a similar way as the primary endpoint, treatment retention rate at injection 2.

## 5.4.2 Secondary endpoints 2 and 3: The proportion of participants reporting adverse events up to Injection 2, and between Injections 2 and 3

The analysis of secondary endpoints 2 and 3 will use the SFAS.

#### **5.4.2.1** Definition of endpoints

These endpoints will encompass all induction attempts, and therefore utilise the first dose of TM BUP for derivations. A treatment-emergent adverse event (TEAE) is defined as an AE having an onset date/time after administration of the first TM BUP dose and before the date/time of Injection 3. The TEAEs are classified into the 2 consecutive time intervals, defined as:

• TEAEs up to RBP-6000 Injection 2 are TEAEs with a start date/time on or after the first dose of TM BUP and before the date/time of Injection 2

 TEAEs between RBP-6000 Injections 2 and 3 are TEAEs with a start date/time on or after Injection 2 and before the date/time of Injection 3

Note: If AE onset time is missing, then only the onset date will be used to assign TEAE status. An AE onset date on or after the date of the administration of the first dose of TM BUP will be considered a TEAE.

For participants who received Injections 1 and 3 (but not Injection 2), their TEAE with start date before the date of Injection 3 will be classified into the time interval of "up to RBP-6000 Injection 2". For discontinued participants whose last injection was Injection 1, their TEAE with start date after the last injection will be classified into the time interval of "up to RBP-6000 Injection 2". For discontinued participants whose last injection was Injection 2, their TEAE with start date after the last injection will be classified into the time interval of "between RBP-6000 Injections 2 and 3".

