4.1.2.2 Standard of Care (SoC) Induction

After completing the pre-TM buprenorphine assessments, participants should then be inducted per SoC according to the applicable TM buprenorphine product labelling

information, that is, a participant should be dose-adjusted onto TM buprenorphine for a minimum of 7 days.

On the first induction day, participants will be asked to remain in the clinic for at least 5 hours after the first TM buprenorphine dose, completing COWS assessments at 1, 2, 3 and 5 hours post TM buprenorphine. All AEs and concomitant medications should be recorded. If the participant experiences exacerbated withdrawal symptoms at any time, he/she may be treated symptomatically.

Prior to the participant leaving the site, the Investigator will be asked to assess the following:

• Did the participant experience precipitated withdrawal after TM buprenorphine, and if so, which AEs were associated with the event?

Any doses of TM buprenorphine administered at the site, dispensed to the participant and taken by the participant outside of the clinic should be recorded. For reconciliation, participants will be asked to return any doses not taken as well as the empty packaging for all doses taken. The Investigator may ask the participant to return for dose adjustment as many times as necessary per SoC, recording any AEs and concomitant medications at each visit.

Participants must meet **all** of the following criteria to receive RBP-6000 using SoC induction:

- 1. The participant has been dose-adjusted onto TM buprenorphine for a minimum of 7 days and, based on the Investigator's judgment, appears eligible for dosing with RBP-6000.
- 2. The participant does not display any allergic/hypersensitivity reaction to TM buprenorphine.
- 3. Based on the Investigator's judgment, the participant did not experience precipitated withdrawal from the most recent TM buprenorphine administration that would prevent RBP-6000 administration.
- 4. Based on the Investigator's judgment, the participant is not sedated (i.e., participant cannot be easily aroused by external stimuli).
- 5. The participant has a negative pregnancy test (if female and of childbearing potential).

If a female participant has a positive pregnancy test, she will be discontinued from the study and will not proceed with subsequent assessments.

assessments will be conducted including (but not limited to) TLFB, COWS,

12-lead ECG, vital signs,

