4.1.3 Second Dose of RBP-6000

The second RBP-6000 dose will be administered at Week 2, 1 week (+4 days) after the first injection.

Participants will be followed up via telephone the day after the second RBP-6000 injections.

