#### 5.1.4 Open-label Induction Sub-study Period

The treatment period for the OLIS begins when the first TM BUP dose is given and ends immediately prior to a participant receiving double-blind RBP-6000 Injection 3. Note that predose assessments for Injection 3 are considered part of the OLIS. See Figure 1 for the OLIS schematic.

For the RI arm, the Induction Day 1 Visit of the most recent induction attempt and the Week 1 Day 1 Visit for the first RBP-6000 injection occur on the same calendar day. In the protocol, this day is the "Day 1" of the RI arm: the RI participants receive their first RBP-6000 injection about 1 hour post TM BUP and then remain on site about 4 hours post injection. The investigator-evaluated PWs occurring within the 1-hour window post TM BUP under Induction Day 1 Visit and those occurring within the 4-hour window post RBP-6000 injection under Week 1 Day 1 Visit are recorded on "Day 1" of the RI arm.

[figure not shown]
For the SoC arm, the Week 1 Day 1 Visit for the first RBP-6000 injection occurs about 7 to 14 days after the Induction Day 1 Visit. At the Induction Day 1 Visit (of the most recent induction attempt), the SoC participants remain on site about 5 hours after the first TM BUP, to serve as the control period for the 5-hour on-site duration post TM BUP on "Day 1" of the RI arm; at Week 1 Day 1 Visit, the SoC participants remain on site about 4 hours post RBP-6000 injection at Week 1 Day 1 Visit, to serve as the control period for the 4-hr on-site duration post injection on "Day 1" of the RI arm.

Therefore, the Induction Day 1 Visit or the Week 1 Day 1 Visit will be used to refer to the "Day 1" of the RI arm, depending on which visit of the SoC arm is to be compared.

Handling of multiple Induction Check-in Days/repeat attempts at induction are described in the analysis sections for the individual endpoints. Example scenarios that may result in multiple Induction Check-in Days/repeated attempts at induction are the following:

- PW from TM BUP that would prevent RBP-6000 administration
- Participant must leave before the in-clinic assessments on an Induction Day Visit are completed

Figure 1. Open-label Induction Sub-study Schematic

BUP=buprenorphine; min=minimum; SoC=standard of care; TM=transmucosal

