### 5.4.2.2 Main analytical approach

The number and proportion of participants with at least 1 TEAE, treatment-related TEAE, serious TEAE, fatal TEAE, serious TEAE meeting LFT criteria, severe TEAE, TEAE leading to discontinuation, or TEAE reported as adverse events of special interest, drug-related hepatic disorders (see definition in Section 6.7.1), injection site reactions (see definition in Section 6.7.2), opioid withdrawal symptoms, and precipitated withdrawal symptoms (per eCRF) will be summarised for each endpoint, by induction arm within randomisation strata and for overall.

The numerator of the proportion for each endpoint will be the number of participants with at least 1 TEAE of interest in the respective time interval. The denominator for endpoint 2 (TEAEs up to RBP-6000 Injection 2) will be the number of participants in the SFAS population. The denominator for endpoint 3 (TEAEs between RBP-6000 Injections 2 and 3) will be the number of the participants in the SFAS population who received Injection 2.

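### Adverse-event percentages up to Injection 2 cover about 7 to 11 days in rapid induction but 14 to 25 days in SoC, so they are not comparable between arms

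*SAP*

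**What the plan says.** - **Start and end of the window.** SAP 5.4.2.1 sets the interval for Secondary Endpoint 2: "TEAEs up to RBP-6000 Injection 2 are TEAEs with a start date/time on or after the first dose of TM BUP". The interval closes at Injection 2. The start is the earliest TM dose even when induction is repeated: "These endpoints will encompass all induction attempts, and therefore utilise the first dose of TM BUP for derivations".
- **First TM dose to Injection 1.** SAP 5.1.4 says of rapid induction that "the RI participants receive their first RBP-6000 injection about 1 hour post TM BUP". Under SoC induction the gap is longer: "the Week 1 Day 1 Visit for the first RBP-6000 injection occurs about 7 to 14 days after the Induction Day 1 Visit". Protocol 4.1.2.2 sets the SoC minimum: "The participant has been dose-adjusted onto TM buprenorphine for a minimum of 7 days and" is judged eligible for injection.
- **Injection 1 to Injection 2, both arms.** Protocol 4.1.3: "The second RBP-6000 dose will be administered at Week 2, 1 week (+4 days) after the first injection".
- **Statistic.** SAP 5.4.2.2 counts participants, not events or days: "The numerator of the proportion for each endpoint will be the number of participants with at least 1 TEAE of interest in the respective time" (that is, in the interval of that endpoint). The base is everyone in the SFAS: "The denominator for endpoint 2 (TEAEs up to RBP-6000 Injection 2) will be the number of participants in the SFAS population". SAP Table 2 labels the analysis descriptive, as counts and percentages.
- **Participants without Injection 2.** Under SAP 5.4.2.1, those who stop after Injection 1 have their later events placed in this interval. Those who miss Injection 2 but receive Injection 3 have everything before Injection 3 placed in it.
- **Related table.** SAP 5.6.2 adds a table of events during the SoC run-in, from first TM dose to Injection 1. No visible table gives SoC events from Injection 1 to Injection 2.

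**The concern.** Two columns headed with the same endpoint cover different lengths of time, and the statistic takes no account of time at risk. A difference between them mixes any real difference in tolerability with the extra week or two of SoC observation. A second distortion comes from the denominator: a SoC participant who leaves during run-in is counted although he or she never had an injection and had a short window.

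This table will be read as a comparison. Section 8.8 of the sub-study appendix (Protocol 22.9) plans the safety summary by induction arm for the period up to Injection 2 and only pooled for the later interval. SAP 5.1.1 and 5.8 carry the secondary endpoints into an interim clinical study report if non-inferiority is declared early and the results are submitted to regulators.

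The run-in table does not repair it. The SoC figure for Injection 1 to Injection 2 cannot be found by subtraction, because one participant can have events in both periods. The SAP does align the arms elsewhere: it defines matched on-site periods of 5 hours after TM dosing and 4 hours after injection (5.1.4), and it lines up withdrawal scores by elapsed time from the TM dose (5.5.3).

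**Working it through.** **1. Check of the time components.** SAP Section 1 puts sub-study participation at up to about 11 weeks, from 30 days of screening, at most 2 weeks of induction and 5 weeks of treatment. (30 + 14 + 35) / 7 = 11.3 weeks, which agrees. In Protocol 22.4 the Injection 2 visit is Day 8 with a window of +4 days, so 7 to 11 days after Day 1.

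**2. Window length, on schedule, one induction attempt.**
- RI: 0 + 7 = 7 days to 0 + 11 = 11 days.
- SoC: 7 + 7 = 14 days to 14 + 11 = 25 days.
- Ratio: 14/7 = 2.0 at the minima and 25/11 = 2.3 at the maxima.

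**3. Events that accrue evenly.** Assume the same constant risk p per week in both arms and no dropout. The expected percentage with at least one event over d days is 1 − exp(−λd), with λ = −ln(1 − p)/7. The documents give no base rate, so p is varied.

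| Assumed p per week | RI, 7 d | RI, 11 d | SoC, 14 d | SoC, 25 d |
|---|---|---|---|---|
| 10% | 10.0% | 15.3% | 19.0% | 31.4% |
| 20% | 20.0% | 29.6% | 36.0% | 54.9% |
| 40% | 40.0% | 55.2% | 64.0% | 83.9% |
| 60% | 60.0% | 76.3% | 84.0% | 96.2% |

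There is no true difference in any row. The 25-day column is an extreme that requires every SoC participant to be at both upper limits.

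**4. Events clustered after each first dose, with SoC run-in loss.** Assume, equally in both arms, a 20% acute risk after the TM start, a 30% acute risk after Injection 1, and a background of 0.01 per day. RI has 7 days and no loss before Injection 1. SoC has 14 days, and a fraction L leaves uninjected, at 3.5 days on average.
- RI: 1 − 0.8 × 0.7 × exp(−0.07) = 47.8%.
- SoC, injected: 1 − 0.8 × 0.7 × exp(−0.14) = 51.3%.
- SoC, left in run-in: 1 − 0.8 × exp(−0.035) = 22.8%.
- SoC overall: (1 − L) × 51.3% + L × 22.8%.

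| L | SoC | SoC minus RI (from unrounded values) |
|---|---|---|
| 0% | 51.3% | +3.5 points |
| 10% | 48.5% | +0.7 |
| 20% | 45.6% | −2.2 |
| 30% | 42.7% | −5.0 |

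The grid was then widened to acute risks of 20/30%, 10/40% and 30/10%, background 0 to 0.02 per day, and L from 0 to 30%. The difference ranges from −10.8 to +7.2 points.

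**5. Injection-site reactions.** These are possible only after an injection. Assume an equal 20% risk per injected participant and no RI loss before Injection 1. RI shows 20%. SoC shows 20% × (1 − L), which is 18%, 16% and 14% at L = 10%, 20% and 30%.

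**6. Whether a person-time rate alone would do.** In the L = 0 case of step 4, simple division by nominal window length gives 47.8/7 = 6.8 per 100 person-days in RI and 51.3/14 = 3.7 in SoC. With clustered events, the rate penalises RI.

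**The case against.** The strongest reply has four parts.

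- **The direction is not built in.** A reader might infer that the definition favours rapid induction by construction, or that SoC would look about twice as harmful. The documents support neither. Protocol 1.3.1 reports that in the earlier rapid-induction study most participants had their events within 48 hours of the injection. Both arms here contain one TM start and one first injection, so extra days may add little. In the two earlier Phase 3 studies only 65.7% or 72.1% of those starting SoC induction reached the second injection (SAP Section 3), so run-in loss may be substantial. Steps 4 and 5 show that it can reverse the sign. The near-doubling also needs a low base rate: at 60% per week the ratio is 84/60 = 1.4. This part stands in full.
- **The late-event rule is not open-ended.** A reader might infer that participants who stop after Injection 1 are followed without limit. Protocol 10.3 ends collection of new events at the end-of-treatment or early-termination visit, and Protocol 6.7.2 encourages the latter 4 weeks after the last injection. The rule applies to both arms. It does still reach well past 7 to 11 days. Repeat induction, allowed in RI within 30 days of consent, also lengthens some RI windows.
- **The endpoint is descriptive.** Run-in is part of the SoC strategy, so counting its events up to a common milestone is legitimate as a description. That is right, and no test or error rate depends on it. It does not make two columns over different periods comparable.
- **An aligned analysis may exist.** Much of SAP 5.5 is blacked out, so this cannot be excluded. The visible definition would still need a footnote.

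**Conclusion.** The percentages for Secondary Endpoint 2 should not be compared between arms as defined. The unequal windows and the all-SFAS denominator follow directly from the text; the 7-to-11 and 14-to-25-day ranges hold for participants on schedule after one attempt. The SoC upper figure rests on the SAP's approximate 14 days, since the visible protocol sets a minimum but no maximum.

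The effect depends on the category. For events that accrue with time SoC is inflated, for example 20% against 36% under an assumed 20% per week. For injection-related categories SoC is understated if participants leave before Injection 1. The net effect on any-event percentages could have either sign, because the documents give neither event timing nor run-in loss for these arms. No formal conclusion of the sub-study changes. This is a cheap improvement that prevents a foreseeable misreading of the safety table.

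**What to change.** In SAP 5.4.2.2, add one descriptive table by arm, from dates already collected:

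- **(a)** the proportion with at least one TEAE from Injection 1 to Injection 2 among injected participants, with a stated cap for those who do not receive Injection 2 (for example 11 days, the upper limit of the visit window), shown beside the existing SoC run-in table;
- **(b)** the proportion over an equal-length window from the first TM dose, labelled as containing different numbers of injections by arm. A 14-day window normally holds two injections in RI and possibly none in SoC, so it should not stand alone;
- **(c)** exposure-adjusted incidence using actual time at risk, read together with (a) and (b) because events may cluster soon after dosing.

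Use injected participants as the denominator for injection-site and RBP-6000-related categories. Footnote the existing percentages as covering unequal windows.

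The cost is one extra table and a footnote. No single column is free of limits: (a) leaves out run-in, (b) mixes different injection counts, and (c) can penalise the shorter window.

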### 5.4.2.2 Main analytical approach

The number and proportion of participants with at least 1 TEAE, treatment-related TEAE, serious TEAE, fatal TEAE, serious TEAE meeting LFT criteria, severe TEAE, TEAE leading to discontinuation, or TEAE reported as adverse events of special interest, drug-related hepatic disorders (see definition in Section 6.7.1), injection site reactions (see definition in Section 6.7.2), opioid withdrawal symptoms, and precipitated withdrawal symptoms (per eCRF) will be summarised for each endpoint, by induction arm within randomisation strata and for overall.

The numerator of the proportion for each endpoint will be the number of participants with at least 1 TEAE of interest in the respective time interval. The denominator for endpoint 2 (TEAEs up to RBP-6000 Injection 2) will be the number of participants in the SFAS population. The denominator for endpoint 3 (TEAEs between RBP-6000 Injections 2 and 3) will be the number of the participants in the SFAS population who received Injection 2.

#### **5.4.2.3** Supportive Analyses

The number and percentage of participants reporting TEAEs, reporting TEAEs of opioid withdrawal symptoms (per eCRF), or reporting TEAEs leading to TM BUP dose increase by induction arm within randomisation strata and for overall will be tabulated by System Organ Class (SOC) and Preferred term (PT) for the 2 time intervals, separately.

#### 5.5 Exploratory Endpoint(s) Analysis

[figure not shown]
The analyses of exploratory endpoints will use the SFAS.

[figure not shown]

## 5.6 Safety Analyses

## 5.6.1 Extent of Exposure

The extent of exposure analyses will be performed for the SFAS using descriptive statistics.

For both treatment arms, the following summaries will be performed:

• Total number of RBP-6000 injections received in the OLIS (ie, 0-3)

- - Number of participants who received RBP-6000 at each injection (Injections 1 through 3)
  - Total number of induction attempts
  - Total dose of TM BUP on the most recent induction day
  - Total dose of additional (post-injection) TM BUP during the first 5 hours of the most recent induction day

For the RI arm, the following summaries will be performed:

- the total dose of pre-injection TM BUP on the most recent induction day.
- the time elapsed between TM BUP and Injection 1 on the most recent induction day, overall

For the SoC arm, the following summaries will be performed for the participants who received RBP-6000 injection:

- The number of days of dose stabilisation (ie, number of days of SoC Induction with TM BUP prior to the first injection of RBP-6000). The number of days will be calculated as the date of the first dose of TM BUP minus the date of the last dose of TM BUP plus 1. A categorical data summary using categories <7, 7, 8, and >8 will be performed, as well as a continuous data summary.
- The average daily TM BUP dose during the SoC induction phase, calculated as the total cumulative dose divided by the number of days of dose stabilisation.
- The total TM BUP dose on the day prior to first injection of RBP-6000 (Day -1, as collected on the eCRF).

Participants who take TM BUP after Week 1 Day 1 will be presented in a data listing. Use of TM BUP after Week 1 Day 1 is prohibited per the protocol, but if it occurs, the information would be captured on the concomitant medication form of the eCRF.

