#### 5.1.2 Analysis Conventions

For participants who re-screen, only the most recent screening attempt will be included.

Continuous variables will be summarised using descriptive statistics such as mean, standard deviation [SD], median, minimum, and maximum. In addition, geometric mean and coefficient of variation will also be summarised for BUP plasma concentration. Categorical variables will be reported as frequency counts (including number missing) and the percentage of participants in corresponding categories.

Individual participant data will be presented by participant in data listings for the Screened Population unless otherwise specified. Data listings will include all data collected from the initial Screening Visit to Injection 3 Visit (Week 6 Day 36 Visit), including unscheduled and end-of-study visits occurring before reaching Injection 3 (Week 6 Day 36 Visit).

Tables and figures presenting summary data will include scheduled timepoints/visits and assessments only. Figures of individual participant data will include all timepoints/visits, scheduled and unscheduled. Timepoints/visits will be presented chronologically.

Observed data are used for analysis, unless handling of missing data is described otherwise within the analysis description or in Section 6.4.

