#### 5.4.1.1 Definition of endpoints

This analysis will utilise the most recent induction attempt. The time from the first dose of TM BUP to treatment discontinuation will be calculated in days as the date of the last scheduled visit observed during the OLIS minus the date of the first dose of TM BUP (for the most recent induction) +1. Participants receiving RBP-6000 Injection 3 will be censored administratively at the end of the OLIS, and the corresponding censor time will be calculated as the date of Injection 3 minus the date of the first dose of TM BUP +1.

The population for analysis (ie, the at-risk population at time 0) will be the Evaluable Population for treatment retention/discontinuation.

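### The SAP's day count for standard-of-care TM buprenorphine subtracts the dates in the wrong order, so a k-day course is counted as 2 − k days

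*SAP*

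**What the plan says.** SAP 5.6.1 (Extent of Exposure) lists three summaries for SoC participants who received RBP-6000. The first is the days of dose stabilisation, which the bullet explains in words as the "number of days of SoC Induction with TM BUP prior to the first injection of RBP-6000". The same bullet gives the derivation as "calculated as the date of the first dose of TM BUP minus the date of the last dose of TM BUP plus 1" and then sets the presentation: "A categorical data summary using categories <7, 7, 8, and >8 will be performed", alongside a continuous summary. The second summary is the average daily TM buprenorphine dose, "calculated as the total cumulative dose divided by the number of days of dose stabilisation", so it takes its divisor from the first.

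Two other places show what the count should look like. SAP 5.1.4 says that in the SoC arm the first "injection occurs about 7 to 14 days after the Induction Day 1 Visit". SAP 5.4.1.1 derives time to discontinuation in the usual order, as "the date of the last scheduled visit observed during the OLIS minus the date of the first dose of TM BUP", plus 1, and the censoring time there is built the same way from the date of Injection 3.

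**The concern.** A duration counted inclusively is the later date minus the earlier date, plus 1. The 5.6.1 formula takes the earlier date first. The result conflicts with the bullet's own description, with its categories and with the order used in 5.4.1.1.

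The SoC arm is defined by a minimum of 7 days on TM buprenorphine (Protocol 4.1.2.2), and this table is the planned description of how long participants actually took it. Programmed literally, it would suggest that no SoC participant who received RBP-6000 had reached 7 days. Courses that really were short could not be told apart by category from courses that met the minimum. The average daily dose for the arm would come out negative.

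**Working it through.** The plan gives no numerical result for this count, so there is no stated figure to reproduce. The check is date arithmetic.

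**Inputs.** The day-count formula, the categories and the divisor come from SAP 5.6.1. The 7-day minimum comes from Protocol 4.1.2.2, and the expected 7 to 14 days from SAP 5.1.4. Let k be the number of calendar days from first to last TM buprenorphine dose, both included.

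**Day count.** Put the first dose on day 1 and the last on day k.

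- As written: first − last + 1 = 1 − k + 1 = 2 − k.
- Usual order: last − first + 1 = k − 1 + 1 = k.

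With dates: first dose 1 June and last dose 7 June give 1 − 7 + 1 = −5 as written, and 7 − 1 + 1 = 7 in the usual order.

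**Average daily dose.** If the true average is A, the cumulative dose is kA. As written, the summary is kA/(2 − k), which is A multiplied by k/(2 − k).

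| True days k | Days as written (2 − k) | Category as written | Correct category | Average dose as written ÷ true, k/(2 − k) |
|---|---|---|---|---|
| 1 | 1 | below 7 | below 7 | 1/1 = 1 |
| 2 | 0 | below 7 | below 7 | 2/0, undefined |
| 3 | −1 | below 7 | below 7 | 3/(−1) = −3.00 |
| 7 | −5 | below 7 | 7 | 7/(−5) = −1.40 |
| 8 | −6 | below 7 | 8 | 8/(−6) = −1.33 |
| 14 | −12 | below 7 | above 8 | 14/(−12) = −1.17 |

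Only k = 1 comes out right.

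**Continuous summary.** Because the result is 2 − k, the mean and median become 2 minus their true values and the SD is unchanged. The minimum becomes 2 minus the true maximum, and the maximum 2 minus the true minimum. As an illustration only, take one course of each length from 7 to 14 days. The true mean is 84/8 = 10.5 with range 7 to 14. The formula gives 2 − 10.5 = −8.5 with range −12 to −5. This takes the 7 to 14 days of SAP 5.1.4 and assumes that the last TM dose is on the day before injection. If it is on the injection day, k runs from 8 to 15 and the formula gives −6 to −13.

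**Other readings of the sentence.** Adding the 1 to the last dose date before subtracting gives first − (last + 1) = −k, which is still negative. Dropping the minus sign gives k − 2 for courses of 2 days or more, so 7 days would appear as 5. Neither reading recovers k.

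**The case against.** The best counter-argument is that the slip corrects itself. The bullet states in words what is being counted, the categories make sense only for a positive number, and 5.4.1.1 has the right order twice. A programmer would see negative days and negative daily doses in the first output. The specifications for tables, listings and figures are in a separate document (SAP section 1) that is not available here, so it is not shown that anyone programmed the literal formula.

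Most of this stands, and it is why the point is minor: the harm is conditional and the intention is not in doubt. It does not make the sentence right. The SAP is what outputs are checked against, and a silent correction would leave the program and the plan in disagreement. The sentence is part of version 3.0, whose version history (SAP Table 1) lists changes to 5.6.1, and nothing elsewhere in either document overrides it.

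A second objection concerns repeated inductions, and it also has force. The bullet does not say which attempt supplies the first dose, and the SAP has no single convention. Section 5.4.1.1 and some 5.6.1 bullets, such as "Total dose of TM BUP on the most recent induction day", use the most recent attempt. The adverse event endpoints in 5.4.2.1 and the concomitant medication summary in 5.7.1 cover all attempts. This is therefore a question for the sponsor and not a further error.

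**Conclusion.** The formula is wrong as written. It returns 2 − k days for a k-day course, leaves three of its four categories empty, and makes the average daily dose negative for every course that meets the 7-day minimum. This follows from the wording alone and does not depend on how course lengths are distributed. The consequences for the output assume literal programming.

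The effect is confined to the SoC day count (categorical and continuous) and the SoC average daily dose, both descriptive. The primary retention analysis, type I error, power, analysis populations, Kaplan-Meier and Cox analyses and adverse event windows do not use this variable. Nor does the 7-day criterion that investigators apply. Severity is minor: an erratum to correct before programming.

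**What to change.** In SAP 5.6.1, define the number of days as the date of the last TM buprenorphine dose before Injection 1, minus the date of the first TM buprenorphine dose, plus 1. The limit to doses before Injection 1 matters because the same section anticipates that some participants may take TM buprenorphine after Week 1 Day 1. Use this value as the divisor of the average daily dose, and sum the cumulative dose over the same interval.

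The sponsor should also state which induction attempt supplies the first dose when induction is repeated. The most recent attempt would agree with 5.4.1.1 and with those 5.6.1 bullets that name an attempt in that way.

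The cost is a one-line SAP correction and the matching line of code. No new data are needed, and the design and primary analysis are unchanged.
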